### **STEP 5: Intervention Period (12 weeks)**

*Exercise Snacks Group (referred to as “high-intensity movement breaks” in the consent form)* – Participants will be prescribed 3-4 exercise snacks performed periodically throughout the day (at the participants discretion to fit their daily schedules based on the onboarding session) on 3-4 days per week. Our lab-based studies used 3 snacks per day for 3 days per week but we have included flexibility in prescription for real-world application. Snack duration, complexity and/or intensity will be increased over the course of the intervention to facilitate progression and accommodate increases in fitness. These adjustments have been designed by the research team in consultation with the Seven Movements team who have a track record of designing “activity breaks” for previously inactive adults in real-world settings. Exercises will be tailored to participant preferences, physical abilities, and environments and include body-weight exercises (e.g., marching in place, step ups, jumping jacks, air squats, lunges), stair-climbing and other aerobically conditioning activities designed to increase heart rate. Instructional videos developed by Seven Movements will be provided for each exercise ensuring participants are comfortable performing the movements safely and effectively.

*Placebo Exercise Control (referred to as “low-intensity movement breaks” in the consent form)*

– An identical intervention delivery approach including the same technology and pre-trial virtual planning/onboarding sessions will be implemented for the placebo group with the exercise snacks being replaced with mobility/stretching based-exercises designed not to stimulate

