## Research Protocol

increases in heart rate and CRF. We selected this as the most appropriate control group in attempts to balance randomization expectations, retention, and ethical considerations compared to a true “hands off” or “no exercise” control.

Technology – Participants will be able to log the timing, duration, and number of exercise snacks completed daily as well as the perceived effort (Borg CR-10 scale) and enjoyment (Exercise Enjoyment Scale) of each snack into the platform. Participants will also be sent weekly self-report adherence surveys via email RedCap link wherein adherence will be assessed by asking participants the total number of snacks completed each week. If participants miss the weekly adherence self-assessment, we will follow-up with an email reminder and (if necessary) a follow-up telephone call to help address any concerns/issues that may have prevented them from completing the weekly assessment. To characterize exercise adherence and track changes in daily physical activity, sedentary time, and sleep patterns, we will provide participants with validated thigh-worn triaxial accelerometers (activPAL4) in line with our previous work. Accelerometer data will be obtained during two, separate 7-day periods (intervention weeks 2 and 11) and extrapolated to the rest of the intervention. As exercise adherence generally diminishes over an intervention, obtaining this data during both early and late stages of the intervention will provide valuable information relating to changes in adherence over the intervention.

Virtual check-ins: To help participants complete their customized movement break plan and to address any potential barriers/challenges that you may encounter of the course of the intervention, we will conduct virtual (phone or zoom) sessions at the 4 and 8 week point of the

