### BACKGROUND AND AIM:

From November 2022 to December 5, 2023, we completed the randomized clinical trial titled “Efficacy of Movement Breaks in Real-World Settings” at two study sites, McMaster University (Mac) and the University of British Columbia (UBC). The purpose of the study was to determine the efficacy of performing movement breaks as either vigorous-intensity “exercise snacks” (ES) or low-intensity mobility-based control activities (CTL) on indices of cardiometabolic health. All movement breaks involved ≤60-second bouts of activity performed periodically throughout the day. Participants in both groups were given access to a web platform that provided individualized notifications to remind them to complete their ES or CTL bouts at least 3 times per day on at least 3 days per week (i.e., minimum prescription of 9 movement breaks per week). Identical scripted counselling at baseline, week 4, and week 8 assisted with individualization and progression of the two movement break prescriptions. Exercise prescription progression and variety were accomplished by altering the exercises in weeks 1-4 (Phase 1), weeks 5-8 (Phase 2), and weeks 9-12 (Phase 3). The primary outcome measure was change from baseline in cardiorespiratory fitness (CRF; assessed via cycling VO2peak test) following the 12-week exercise intervention. Secondary outcomes included changes in basic anthropometric measures (body mass and waist circumference); fasting plasma insulin, glucose, homeostasis model assessment of insulin resistance (HOMA-IR), and inflammatory cytokines; device-measured and self-reported adherence to movement breaks; and enjoyment and perceived exertion following movement breaks. It was hypothesized that a 12-week technology-enabled real-world ES intervention would improve CRF as compared to CTL in previously inactive adults.

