**Secondary outcome measures:** To supplement the primary outcome of VO2peak in mL/kg/min we will also analyze peak power output and absolute VO2peak (L/min). Key secondary outcomes will include exercise adherence, enjoyment, and perceived exertion assessed by self-report. Self-reported adherence to the intervention will be determined by user analytics on the Seven Movements platform and using the automated weekly REDCap surveys. We will define high, moderate, or low adherence as completing >67%, 50-66% or <50% of the prescribed intervention (i.e., total # of snacks performed relative to minimum prescription of 9 snacks per week and the number of days when participants completed  $\geq 3$  snacks relative to a prescription of 3 days per week). Enjoyment (Exercise Enjoyment Scale) and perceived exertion (Borg CR-10 scale) will be asked following each snack. Adherence, enjoyment, and exertion data will be analyzed using a linear mixed model that will include fixed effects for group (ES vs. CTL), timepoint (week, Phase or session number), their interaction, and stratified allocation factors (site, sex) and random effects for participants. In these analyses, the main effect of group will be most important to identify an overall effect of the intervention on these variables.

Other continuous secondary outcomes assessed at baseline and a follow-up timepoint will be analyzed similarly to the primary outcome using a constrained baseline longitudinal data analysis linear mixed model (with all relevant follow-up timepoints included as a fixed factor of time in the model). Secondary outcomes include:

- Changes in anthropometrics assessed at baseline and 12-weeks.
- Changes in blood markers (fasting plasma glucose, insulin, HOMA-IR, inflammatory cytokines) assessed at baseline and 12 weeks.

- Changes in hematology analysis of complete blood count (total white blood cells, hematocrit, hemoglobin, monocytes, neutrophils) assessed at baseline and 12-weeks.
- Changes in device-worn physical activity and sedentary time assessed at baseline, week 2, and week 11 via device-worn measurement.
- Changes in leisure time physical activity assessed by GLTEQ measured at baseline and 12 weeks.

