### **SENSITIVITY ANALYSIS:**

We will perform per-protocol sensitivity analyses on the primary outcome (change in VO2peak at 12 weeks) and secondary outcomes. To be included in these analyses, participants will need to have baseline and week 12 measurements for the outcome of interest and have completed >67% of the prescribed exercise intervention (“high” adherence, equivalent to 6 movement breaks per week, or 72 total exercise snacks)

Within-group changes from baseline for all outcomes will be reported as derived from the model employed for the primary (between-group) analyses outlined above

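### Session number, as a permitted time axis for the per-snack enjoyment and exertion ratings, depends on adherence; Phase or calendar week should be named instead

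*SAP*

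**What the plan says.** Under Secondary outcome measures, the SAP gives adherence, enjoyment and exertion a single linear mixed model. It has fixed effects for group, "timepoint (week, Phase or session number), their interaction, and stratified allocation factors (site, sex"), plus random effects for participants. The text does not assign an axis to each outcome. It also does not say whether time is numeric or categorical, or what the group term means once the interaction is in the model. It does rank the contrasts: "the main effect of group will be most important to identify an overall effect of the intervention on these variables".

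The other relevant statements are these:

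- **Rating times** (same SAP paragraph): "Enjoyment (Exercise Enjoyment Scale) and perceived exertion (Borg CR-10 scale) will be asked following each snack".
- **Progression** (SAP, Background and Aim): the exercises progress by "altering the exercises in weeks 1-4 (Phase 1), weeks 5-8 (Phase 2), and weeks 9-12 (Phase 3"). These are calendar blocks.
- **Dose**: the SAP sets a "minimum prescription of 9 movement breaks per week". The Protocol (Step 5) says "Participants will be prescribed 3-4 exercise snacks performed periodically throughout the day", on 3-4 days a week.
- **High adherence** (SAP, Sensitivity Analysis): "equivalent to 6 movement breaks per week, or 72 total exercise snacks".
- **Expected course of adherence** (Protocol, Step 5, Technology): "As exercise adherence generally diminishes over an intervention". The same paragraph says participants can log the timing of each snack.

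Neither document gives adherence by arm or an expected course for the ratings.

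**The concern.** A rating exists only when a break has been done. A participant's session number on a given date is therefore cumulative adherence, a post-randomisation variable that the trial also compares between arms. Lining participants up by session number puts people in different weeks, doing different exercises, at the same point on the time axis.

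Suppose enjoyment followed the same weekly course in both arms, but one arm did fewer breaks. Plotted by session, that arm would seem to change faster and would differ at a matched session number. The report could then say that vigorous snacks lose enjoyment faster, or are less enjoyable, than mobility breaks when only the number of breaks differed. That would bear on the feasibility part of the Protocol's Project Aim.

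**Working it through.** **1. The plan's own figure.** High adherence: 6 × 12 = 72 breaks. Minimum prescription: 9 × 12 = 108. Ratio: 72/108 = 66.7%, which agrees with the SAP's 67% threshold. The Protocol range is 3 × 3 = 9 to 4 × 4 = 16 per week.

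**2. Where a session falls.** At a steady rate, week = ceil(session/rate) and Phase = ceil(week/4).

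| Session | 6 per week | 9 per week | 16 per week |
|---|---|---|---|
| 36 | week 6, Phase 2 | week 4, Phase 1 | week 3, Phase 1 |
| 54 | week 9, Phase 3 | week 6, Phase 2 | week 4, Phase 1 |
| 72 | week 12, Phase 3 | week 8, Phase 2 | week 5, Phase 2 |

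Sessions 73 to 108 do not exist for someone at 6 per week.

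**3. Size by hand.** Let ratings fall 0.5 points per Phase in both arms, with no arm difference in any week. At session 54 a participant at 6 per week has fallen 2 × 0.5 = 1.0, and one at 9 per week has fallen 1 × 0.5 = 0.5. The apparent difference is 0.5 points.

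**4. Simulation.** There is no true arm difference at any calendar week. Rates, SDs and Phase changes are assumptions. The designs are:

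- *S1*: 30 per arm, 1000 trials. Each participant's slope and value at session 54 were estimated and compared by Welch t-test. Between-participant rate SD 2, intercept SD 1, trend SD 0.7 over 12 weeks, residual SD 1.
- *S2*: mixed model with random slopes, 30 per arm, 60 replicates.
- *S3*: mixed model with random slopes and centred session number, S1's data assumptions, 100 replicates.
- *S4*: mixed model with random intercept only, 40 per arm, 100 replicates, rate SD 3. Ratings rise rather than fall.

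Results at 6 versus 9 breaks per week, as the share of trials with p < 0.05:

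| Change per Phase | Design | Interaction, session axis | Group effect, session axis | Calendar week (interaction; group) |
|---|---|---|---|---|
| 0 | S4 | 2% | 6% | 5%; 6% |
| 0.25 | S1 | 20% | not computed | 4-6% (interaction) |
| 0.25 | S2 | 17% | not clearly inflated | not listed |
| 0.25 | S3 | not listed | 6% | 3% (group) |
| 0.5 | S1 | 57% | bias 0.43 points at session 54 | 4-6% (interaction) |
| 0.5 | S2 | 57% | 25% (0.38 points) | 3%; 8% |
| 0.5 | S3 | not listed | 21% | not listed |
| 0.5 | S4 | 83% | 17% (0.21 points) | 2%; 6% |

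A 500-trial repeat of S1 at 0.5 points gave 53% for the interaction.

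Monte Carlo error: for S2, √(0.57 × 0.43/60) = 6.4 percentage points for the interaction and √(0.25 × 0.75/60) = 5.6 for the group effect. For S3, √(0.21 × 0.79/100) = 4.1. The 21% and 25% are therefore compatible.

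**5. Other adherence gaps.**

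- 7 versus 9 per week: S1 interaction 31% (0.5 points) and 12% (0.25); S3 group effect 13% and 7%.
- 9 versus 12: S1 interaction 43% and 16%.
- 8 versus 9 at 0.25 points, mixed model with random slopes: both tests near nominal (7% and 6%).
- 9 versus 9: no inflation in S1. In S4 the interaction averages about 0 but is rejected in 20%, because a random intercept alone ignores participants' different slopes per session.

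**6. Who supplies the late sessions.** With rate SD 3, 69%, 50% and 17% of an arm averaging 6 per week reach sessions 54, 72 and 108. At an average of 9 the figures are 93%, 84% and 50%. To test whether this alone biases the trend, S4 was run with flat ratings and a 0.5 correlation between rating level and exercise frequency. The interaction was rejected in 4%.

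**The case against.** The strongest reply is that a false trend needs two conditions that the documents do not establish: adherence that differs between arms, and ratings that move with calendar time. A reader might infer that any adherence difference produces different trends by construction. That is not so: flat ratings gave 2% rejection at 6 versus 9, and equal adherence gave no inflation once participant slopes were allowed for. The Protocol's remark on declining adherence does not say that the arms differ, and both arms get the same delivery and counselling. This part of the reply stands, so the point is conditional.

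A reader might also infer that the loss of infrequent exercisers from late sessions is itself the source of bias. Selection on rating level gave no false trend, because the random intercept absorbs it. Selection on a participant's own trend was not tested. The coverage figures describe the data and do not show bias.

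Third, the SAP puts the group main effect first, and that effect is more robust: near nominal at 0.25 points per Phase and clearly shifted only at 0.5. This limits the weight of the point but does not remove it, because the interaction is also in the model and the main effect is not immune.

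Fourth, session number is one of three options, and the SAP does not tie it to enjoyment and exertion. That link is an inference from per-snack rating, though a natural one. Response to the k-th exposure is also a fair question about habituation, so session number need not be banned outright.

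**Conclusion.** The point holds conditionally. The misalignment between session number and calendar Phase is arithmetic, and it makes the axis a function of adherence. Bias follows if session number is chosen, the arms differ in adherence, and ratings change over calendar time or Phase. The planned change of exercises makes the last condition plausible, but the documents do not show it.

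At an assumed 6 versus 9 breaks per week with participant slopes allowed for, the false interaction rate is roughly 55% for a 0.5-point change per Phase and 17-20% for 0.25. The false group-effect rate is roughly 20-25% and near nominal respectively. With small adherence gaps and small changes there is little effect. Centring session number and fitting random slopes does not cure the problem, because those settings were used in these results.

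The documents do not support reading this as a flaw in the trial's main result. It concerns two secondary ratings, and the primary VO2peak model uses only baseline and week 12.

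**What to change.** In the SAP's Secondary outcome measures paragraph:

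1. For enjoyment and exertion, name Phase or calendar week as the time factor, choosing one in advance.
2. Assign each rating to the week in which its snack was logged, using the timing recorded in the platform.
3. Define the group effect as the average over Phases or weeks.
4. Report the number of participants contributing ratings, by arm and Phase.
5. Label any session-number analysis supplementary and descriptive.

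Both recommended axes are already among the SAP's options, and the Protocol already provides for logging the timing, so no new data are needed. The cost is a few lines of text and a coarser time scale than session number. The choice should be fixed while the analysis is still blinded to allocation, as the SAP intends.

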### Outcomes

| Category                                       | Variable   | Timepoints                    |
|--|--|-------------------------------|
| Anthropomorphic Measures                       | Weight, Waist circumference, body mass index (BMI)   | Baseline, 12 weeks            |
| Blood Pressure                                 | Systolic, Diastolic, Mean Arterial Pressure  | Baseline, 12 weeks            |
| Blood Biochemistry                             | Fasting plasma insulin, fasting plasma glucose, HOMA-IR, fasting plasma cytokines  | Baseline, 12 weeks            |
| Complete Blood Count                           | Total White Blood Cells, Hematocrit, Hemoglobin, Monocytes, Neutrophils  | Baseline, 12 weeks            |
| Exercise Behavior (GLTEQ)                      | Bouts of mild, moderate, and strenuous exercise lasting >15min, weekly leisure-time exercise   | Baseline, 12 weeks            |
| Cardiorespiratory Fitness                      | Cycling? VO 2 peak, max HR, peak RER, peak power output (W)   | Baseline, 12 weeks            |
| Movement Break Adherence (Device-worn)         | Device wear time, average minutes per day of total, light, moderate, vigorous, and moderate-vigorous physical activity per day, average minutes of sedentary time per date, sit-to-stand ratio per day | Baseline, week 2 and, week 11 |
| Movement Break Adherence (Self-report)         | Weekly surveys assessing number of movement breaks completed   | Weekly for 12 weeks           |
| Movement Break Adherence (technology platform) | Number of movement breaks completed within the Seven Movements account   | Recorded for each snack       |
| EES  | Exercise enjoyment
1 (Not at all)
2 (Very light)
3 (Slightly)
4 (Moderately)
5 (Quite a bit)
6 (Very much)
7 (Extremely)  | Following each snack          |
| Borg CR-10 scale                               | Rating of perceived exertion
0 (Rest)
1 (Very, very easy)
2 (Easy)
3 (Moderate)
4 (Somewhat hard)
5 (Hard)
6
7 (Very hard)   | Following each snack          |

|  |                        |  |
|--|------------------------|--|
|  | 8
9
10 (Maximal) |  |
|--|------------------------|--|

**Primary outcome:** The prespecified primary outcome for this trial will be a comparison of the change in VO2peak (mL/kg/min) from baseline to 12 weeks between the movement break intervention groups.

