The primary data analyses will be intention-to-treat. Data will be analyzed by constrained longitudinal data analysis (cLDA) via a linear mixed model with fixed effects for timepoint (i.e., baseline and week 12), the interaction between timepoint and intervention group (i.e., ES or CTL), and stratified allocation factors (sex, study site) as well as random effects for participants to account for the correlation of repeated measures within participants. The between-group treatment (interaction) effect estimate at 12 weeks with 95% confidence intervals will be reported as the main analyses of interest. Significance will be set at  $p<0.05$  and Cohen's d effect sizes will be calculated to estimate the magnitude of between-group differences in pre-post change scores.

The cLDA approach constrains the baseline means to be equal between the treatment groups, which is a reasonable assumption in the context of a randomized clinical trial. No missing data will be imputed as per contemporary guidelines [3]. Model specification will be assessed visually using normal probability plots and residuals vs. fitted values plots. Models will be run using log-transformed outcome variables when departure from model assumptions is observed.

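### The overall group effect for adherence, enjoyment and exertion is not defined as a contrast, and one permitted time axis (session number) does not readily yield it

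*SAP*

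**What the plan says.** The SAP's Secondary outcome measures paragraph names adherence, enjoyment and perceived exertion as key secondary outcomes. Each is to be analysed by a linear mixed model with "fixed effects for group (ES vs. CTL), timepoint (week, Phase or session number), their interaction", plus site, sex and a random participant effect. The result to be relied on is then stated: "In these analyses, the main effect of group will be most important to identify an overall effect of the intervention on these variables".

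For these three outcomes the SAP does not say:
- which time variable goes with which outcome;
- whether time is a factor or numeric, or whether it is centred;
- how factors are coded, or which type of test is used;
- whether marginal means are averaged over time, and with what weights.

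The SAP is more exact elsewhere. For the primary outcome it names the contrast and the timepoint: "The between-group treatment (interaction) effect estimate at 12 weeks with 95% confidence intervals will be reported as the main analyses of interest". For the other continuous secondary outcomes it says that time enters as a factor. The protocol's Statistical Analysis section does not fill the gap: it describes one mixed model for all quantitative outcomes and points to the between-group effect at 12 weeks.

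Two passages bear on change over time. The protocol (STEP 5, Technology) says: "As exercise adherence generally diminishes over an intervention". The SAP (Background and Aim) says that the exercises changed across three four-week Phases.

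**The concern.** Once a group-by-time interaction is in the model, the group term has no single meaning. It is the arm difference at whatever point in time the coding sets to zero. That can be an average over the intervention, the first week or Phase, or a session 0 that does not exist. The SAP wants an overall effect but does not fix the coding or contrast that would deliver it.

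These outcomes carry the trial's message on acceptability. If the arm difference changes over 12 weeks, a term read at the start can miss a difference that builds up, overstate one that fades, or declare one where the average is nil. Even with a constant difference, the start-of-trial term is less precise than the average. Leaving the time axis and coding open also leaves a choice of results to the analysis stage.

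**Working it through.** The documents give no figure for these models, so there is none to reproduce. The check has four parts.

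**1. What the group term is.** Let D(t) be the ES-minus-CTL difference at time t.
- Numeric time: D(t) = b + c·t, so b = D(0). Coding group as 0/1 or as ±½ leaves b = D(0), because the coding of group does not move the zero of time. Centring time at its mean turns b into D(mean time), which is the average in balanced data.
- Time as a factor: D_k = b + c_k. With c_1 = 0 (reference coding), b = D_1. With the c_k summing to zero, b is the mean of the D_k.

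**2. Adherence by week.** From the documents: 12 weekly surveys (SAP Outcomes table), and 30 or 40 per group (SAP sample size section). Assumed: between-person SD 2 and residual SD 2 breaks/week, balanced data, two-sided 0.05. With n per group, mean week 6.5 and sum of squares 143:
- average: variance = (2/n)(2² + 2²/12); at n=40 this is 0.217, SE 0.47
- week 1: variance = (2/n)(2² + 2²); 0.400, SE 0.63
- time 0: variance = average variance + (2/n)·2²·6.5²/143; 0.217 + 0.059 = 0.276, SE 0.53

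Target of each term at 40 per group, with the rejection rate in brackets:

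| Assumed difference, week 1 to week 12 | Week-1 term | Time-0 term | Average |
|---|---|---|---|
| 0 to -3 | 0.00 (0.05) | +0.27 (0.08) | -1.50 (0.90) |
| -3 to 0 | -3.00 (1.00) | -3.27 (1.00) | -1.50 (0.90) |
| +1.5 to -1.5 | +1.50 (0.66) | +1.77 (0.92) | 0.00 (0.05) |
| constant -1.5 | -1.50 (0.66) | -1.50 (0.81) | -1.50 (0.90) |

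At 30 per group, power for an average of -1.50 is 0.80. With a constant difference the three powers are 0.54, 0.70 and 0.80.

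Wider assumptions: between-person SD 3, residual SD 2, person-slope SD 0.2 per week, equal start, divergence of 0.3 breaks/week. The average difference is 0.3 × 5.5 = 1.65. The variance of a person's mean is 9 + 0.2² × 5.5² + 4/12 = 10.54, so the SE is √(2 × 10.54/40) = 0.73 or √(2 × 10.54/30) = 0.84. Power for the average is about 62% or 50%. In 4,000 simulated trials per scenario, the group coefficient read at the start rejected in 3-4%.

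**3. One data set, one model, different codings.** Simulated with 40 per group, 12 weeks, the SDs of part 2 and a difference growing from 0 to -3; fitted by maximum likelihood.

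| Time | Coding | Group term (SE) | p | Log-likelihood |
|---|---|---|---|---|
| Week as factor | reference | -0.65 (0.64) | 0.31 | -2108.571 |
| Week as factor | sum-to-zero | -1.93 (0.49) | 0.00008 | -2108.571 |
| Linear week | uncentred | -0.14 (0.54) | 0.80 | -2115.333 |
| Linear week | centred | -1.93 (0.49) | 0.00008 | -2115.333 |

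Within each pair the fit is identical. Only the meaning of the reported row changes.

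**4. Session number.**
- *Numeric, uncentred.* Assume exertion of 4, 5 and 6 by Phase under ES and 1.5 throughout under CTL, with 108 sessions each (9 per week × 12). The differences are 2.5, 3.5 and 4.5, averaging 3.5. The least-squares slope is 2 × 36 × 36 / 104,967 = 0.0247 per session. The value at session 0 is 3.5 - 0.0247 × 54.5 = 2.15, which is 39% too small. A Type III test does not help, because the covariate is still evaluated at zero.
- *Numeric, centred.* Participants complete different numbers of sessions, so the centre and the weights depend on adherence, itself one of the outcomes.
- *Factor.* In a simulated case with arm maxima of 165 and 158 sessions, the group-by-session design has 2 × 165 = 330 columns but only 165 + 158 = 323 occupied cells. Its rank is 323, and the group effect averaged over all sessions is not estimable.

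**The case against.** The strongest reply is that a main effect beside an interaction ordinarily means the effect averaged over the other factor, and that the SAP's stated aim of an overall effect confirms this. That stands for week and Phase. A reader might infer that the planned group term simply is the week-1 or session-0 difference, so that the test is wrong. The documents do not support that: nothing in them says a reference-coded coefficient will be reported, and sum-to-zero coding, marginal means, or centred time in balanced data all recover the average.

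A reader might also infer that the documents predict diverging arms. They do not. The protocol says that adherence falls, not that it falls differently by arm. The SAP describes progression of both prescriptions with the same scripted counselling. Exertion differs by design from the first snack, so the picture of arms that start alike does not suit that outcome. If the difference is constant, every coding targets the same value and only precision is lost.

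It is fair too that the trajectories and SDs are chosen, that the interaction is already in the model, and that the separate high/moderate/low adherence classes would show part of a sustained gap.

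What the reply does not answer is session number. The SAP allows it, and it is the natural index for ratings taken after each snack. Uncentred, it gives a session-0 difference; as a factor, it can leave the average non-estimable. Nor does the reply remove the need to state the contrast for week and Phase.

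**Conclusion.** The point holds as an undefined contrast on the key secondary outcomes, with a specific fault if session number is the time axis. It is not a demonstrably wrong test for week or Phase.

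That the group term depends on coding is algebra and needs no assumptions. How much it matters depends on how the arm difference moves over time, which the documents make plausible but do not state. Under the assumed patterns, the reported term ranges from no effect when the average is -1.50 breaks/week, through double that average (-3.00), to a spurious +1.50 or +1.77 when the average is zero. For exertion the illustration is 2.15 against 3.5 points, in the right direction but too small. These are illustrations, not forecasts. The primary outcome is unaffected, because its contrast is stated. The change should be made, but it does not bear on the trial's main conclusion.

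**What to change.** In the SAP's Secondary outcome measures paragraph, replace the reliance on the main effect of group with a defined contrast: the ES-minus-CTL difference in estimated marginal means, averaged equally over weeks 1-12 for adherence and over Phases 1-3 for enjoyment and exertion, with its 95% CI. Enter week (adherence) or Phase (ratings) as a factor, and remove session number as a time axis. Report the group-by-time interaction alongside, since an average is only a summary when the difference changes.

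Equal weighting is a choice. It matches the stated aim of an overall effect and does not let the weights depend on how many sessions each participant logged. Whatever weights are used should be written down before results by arm are seen.

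The cost is about two sentences in the SAP and one contrast statement in the code. No new data are needed.
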